## 8.6. Replacement of Subjects

If a subject discontinues or is discontinued at the discretion of the investigator or DMC up to and including the Week 12 visit, the subject may be replaced with another subject meeting the eligibility criteria; up to 10 subjects for Population 1 and up to 10 subjects for Population 2 may be replaced. Refer to Section 7 for details about randomization and treatment assignments. Refer to Section 8.5 for guidelines on study drug dose withholding and discontinuation and to Section 8.4 for guidelines on withdrawal of subjects from study participation. All data collected prior to withdrawal must be recorded in the replaced subject's eCRF.

## 8.7. Stopping Rules and Study Termination

It is anticipated that AEs will occur frequently in this population based on the underlying disease, and that these can also be SAEs. There is no predefined type or frequency of AEs or SAEs for a stopping rule in this study. Review of SAEs and deaths on study will be performed routinely by the DMC, as defined in this protocol and in the DMC charter.

If a safety concern arises that warrants review for possible study termination, the DMC (or party identifying such concern) will notify the sponsor immediately. Enrollment in the study may be temporarily halted for further review of safety data. This further assessment of safety and/or preliminary efficacy data will include review by the DMC, which may include the recommendation to terminate the study early or stop a treatment arm for safety or lack of efficacy, as outlined in the DMC charter.

Termination of the clinical study may also occur due to a regulatory authority decision or if the sponsor or regulatory authority decides that subject safety may be compromised by continuing the study.

If the study is halted temporarily or prematurely terminated, a written statement fully documenting the reasons for study halt or termination will be provided to the Institutional Review Board (IRB)/Independent Ethics Committee (IEC) and appropriate regulatory authorities.

## **9. STUDY TREATMENTS**

### **9.1. Storage Conditions**

Upon receipt of the study drug, an inventory must be performed, and a drug receipt log completed and signed by the person accepting the shipment. It is important that the designated study staff counts and verifies that the shipment contains all the items noted in the shipment inventory.

Only subjects enrolled in the study may receive study drug, and only authorized site staff may supply or administer study drug to subjects. All study drug must be stored in a secure, environmentally controlled, and monitored (manual or automatic) location in accordance with the labelled storage conditions and with access limited to the investigator and authorized site staff.

The study site must maintain accurate records demonstrating dates and quantity of study drug received, to whom dispensed (subject-by-subject accounting), any amount returned, and accounts of any study drug that was accidentally destroyed.

### **9.2. Study Drug**

IMR-687 will be supplied as 100, 150, or 200 mg white tablets. Subjects will be advised to take two IMR-687 tablets orally with food qd for 36 weeks. To maintain appropriate exposures, 60 kg will be used as the weight gate for tablet strength. Subjects in the lower dose group weighing <60 kg will be dispensed 100 mg tablets and those weighing  $\geq$ 60 kg will be dispensed 150 mg tablets. Subjects in the higher dose group weighing <60 kg will be dispensed 150 mg tablets and those weighing  $\geq$ 60 kg will be dispensed 200 mg tablets. The different doses of IMR-687 are visually identical in tablet form.

Placebo will consist of tablets containing matrix absent IMR-687 and will be identical in appearance to the IMR-687 tablets. Subjects will be advised to take two placebo tablets orally with food qd for 36 weeks.

Subjects will be directed to take study drug (either IMR-687 or placebo) with food, but if a subject does not do so, it will not be considered a protocol deviation.

### **9.3. Packaging and Labeling**

Finished tablets will be packaged in round, 60 cc high-density polyethylene bottles with a polypropylene cap. Each bottle contains 84 tablets. The bottles are induction sealed and capped. Each bottle will be labelled with a suitable Annex 13 country compliant product label.

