	FA	Over 36 weeks from Baseline	Per Protocol Analysis Set/ ITT (mITT) Analysis Set
Proportion of subjects who are transfusion-free (independent) for ≥ 8 weeks during treatment	IA 2.0	Through Week 24	Per Protocol Analysis Set/ ITT Analysis Set
	FA	Through Week 36	Per Protocol Analysis Set/ ITT (mITT) Analysis Set
Proportion of subjects who are RBC transfusion-free (independent)	IA 2.0	Over 24 weeks	Per Protocol Analysis Set/ ITT Analysis Set
	FA	Over 36 weeks	Per Protocol Analysis Set/ ITT (mITT) Analysis Set
Mean change from Baseline for Serum ferritin	IA 0.5	Week 24	Per Protocol Analysis Set

Outputs	Analysis Number	Timepoints	Analysis Set(s)
	IA 1.0	Week 24	Per Protocol Analysis Set
	IA 2.0	Week 24	Per Protocol Analysis Set/ ITT Analysis Set
	FA	Week 24, 36	Per Protocol Analysis Set/ ITT (mITT) Analysis Set
Mean change from Baseline for Iron chelation therapy daily dose	IA 2.0	Week 24	Per Protocol Analysis Set/ ITT Analysis Set
	FA	Week 24, 36	Per Protocol Analysis Set/ ITT (mITT) Analysis Set
Change from Baseline in SF-36 quality of life	IA 2.0	Weeks 12, 24	ITT Analysis Set
	FA	Weeks 12, 24, 36	ITT (mITT) Analysis set
Change from Baseline in mean NTDT-PRO total score and domain scores including tiredness/weakness domain over a continuous 12-week interval	IA 2.0	Week 12 to Week 24	ITT Analysis Set
	FA	Week 12 to Week 24, Week 24 to Week 36	ITT (mITT) Analysis Set
Change from Baseline in NTDT-PRO total score and domain score including tiredness/weakness domain	IA 2.0	Week 24	ITT Analysis Set
	FA	Weeks 24, 36	ITT (mITT) Analysis Set
Summary of exposure	IA 0.5, 1.0, 2.0	All available data up to Week 24 at the time of IA	Safety Analysis Set
	FA	All available data	Safety Analysis Set
Overall summary of TEAEs	IA 0.5, 1.0, 2.0	All available data up to Week 24 at the time of IA	Safety Analysis Set
	FA	All available data	Safety Analysis Set
TEAEs by SOC & PT	IA 0.5, 1.0, 2.0	All available data up to Week 24 at the time of IA	Safety Analysis Set
	FA	All available data	Safety Analysis Set
TEAEs by PT	IA 0.5, 1.0, 2.0	All available data up to Week 24 at the time of IA	Safety Analysis Set
	FA	All available data	Safety Analysis Set
Drug-related TEAEs by SOC & PT	IA 0.5, 1.0, 2.0	All available data up to Week 24 at the time of IA	Safety Analysis Set
	FA	All available data	Safety Analysis Set
Drug-related TEAEs by PT	IA 0.5, 1.0, 2.0	All available data up to Week 24 at the time of IA	Safety Analysis Set
	FA	All available data	Safety Analysis Set

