13.1 Subject Disposition

The number of subjects screened, screen failed, randomized, and treated in the study will be presented, together with the number and percentage of subjects who completed 24 weeks of treatment, completed 36 weeks of treatment, discontinued study drug, and discontinued from the study will be tabulated. The primary reason for screen failure, study drug discontinuation, and study discontinuation will also be tabulated.

Subjects who completed 24 weeks of treatment are defined as either 1) answered “Yes” to the “Did the subject take study drug dose during clinic visit?” question at the Week 24 visit, or later, on the Study Drug Administration eCRF, or 2) have a non-missing “Start Date of Dose From This Bottle” or “Date of Last

Dose for this Bottle" on the Study Drug Accountability eCRF that is on or after the Week 24 visit. Subjects who completed 36 weeks of treatment are defined similarly relative to the week 36 visit.

Percentages for screen failed, primary reason for screen failure, and randomized will be based on all subjects screened. Percentages for number of subjects treated in the study will be based on all randomized subjects. Percentages for number of subjects who completed 24 weeks of treatment, number of subjects who completed 36 weeks of treatment, number of subjects who discontinued study drug, primary reason for study drug discontinuation, number of subjects discontinued from the study, and the primary reason for study discontinuation will be based on all treated subjects.

Summaries will be based on all subjects screened and tabulated for each treatment arm and the total and will be reported separately for TDT and NTDT subjects.

Tabulation of the number and percentage of subjects included in each analysis set will be provided. All percentages will be based on all randomized subjects, for each treatment arm and the total, and will be reported separately for TDT and NTDT subjects.

Details regarding randomization assignments, replacement of randomized subjects, subjects who discontinued study drug and/or study, and subject analysis sets will be reported in by-subject listings.

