13.3 Treatment

13.3.1 Extent of Study Drug Exposure and Drug Accountability

A summary of exposure and compliance, to be reported on the Safety Analysis Set, will include the total number of tablets taken, compliance (%), total exposure (mg), average daily dose (mg/day), duration of exposure (in weeks), and incidence and duration of dose interruption. These parameters will be calculated as follows:

- Duration of exposure (in weeks) will be calculated as [(date of last dose of study medication – date of first dose of study medication + 1)/7]. The date of first dose of study medication will be collected from the Study Drug Administration CRF page and the date of last dose of study medication will be collected from the End of Treatment CRF page. If there is no date for end of treatment on the End of Treatment CRF page, the last available dose date will be used. See Appendix 3 for a complete set of data handling rules.
- Total number of tablets taken = total number of tablets dispensed – total number of tablets returned. The total number of tablets dispensed and returned will be collected from Study Drug

Accountability CRF Page. They are to be collected at study visits and will be summed over the whole study treatment period.

- Total exposure (mg) of IMR-687 = Total number of tablets taken * tablet dose level (100/150/200 mg). IMR-687 will be supplied as 100, 150, or 200 mg white tablets in the study. In the lower dose group (≥ 3.0 to ≤ 5.0 mg/kg), subjects weighing <60 kg will be dispensed 100 mg tablets and those weighing ≥ 60 kg will be dispensed 150 mg tablets. In the higher dose group (>4.5 to ≤ 6.7 mg/kg), subjects weighing <60 kg will be dispensed 150 mg tablets and those weighing ≥ 60 kg will be dispensed 200 mg tablets. The dose regimen for all subjects is 2 tablets once daily. The weight at the baseline will be used to establish the dose level and the same dose level will be used throughout the trial.
- Incidence and duration of dose interruption: as collected from the IP Interruptions CRF page.
- Overall compliance (%) = $[(\text{total number of tablets dispensed} - \text{total number of tablets returned}) / \text{duration of exposure (days)}] \times 100$.
- Average daily dose (mg/day) = total exposure (mg) / duration of therapy (days).

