Additional considerations and data handling in exposure and drug accountabilities may be needed for the DMC, IA, and final analysis when some of drug dosing and accountability information is deemed incomplete. See Appendix 3 for a complete set of data handling rules for drug exposure and accountability.

The same tabulation will be generated for the PP Analysis set if it is not the same as the Safety Analysis Set.

Details of the administration of study drug, including randomized and actual treatment, start date and time of each dose, dose per administration, and date, time, and composition of last meal will be listed on the Safety Analysis Set.

Details of study drug accountability including date dispensed, date returned, amount returned, and compliance per dosing period (in %, as collected directly from CRF), overall compliance (in %, for the whole duration of study drug exposure, as calculated as above) will be listed based on the Safety Analysis Set.

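### The SAP has no rule for bottles still open at a data cut or never returned; applied as written, its tablet count treats them as fully taken and overstates total exposure

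*Protocol*

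**What the plan says.** SAP 13.3.1 defines the count: "Total number of tablets taken = total number of tablets dispensed – total number of tablets returned". On scope it adds: "They are to be collected at study visits and will be summed over the whole study treatment period". Total mg is this count times tablet strength, and average daily dose is total mg divided by days of therapy. Overall compliance uses the same count.

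The section accepts that accountability may be incomplete at DMC, interim and final analyses, and then refers the reader on: "See Appendix 3 for a complete set of data handling rules for drug exposure and accountability". Appendix 3 covers the first-dose date, the last-dose date and durations. It does not mention tablets or bottles without a return.

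Two rules cover a missing last-dose date. SAP 13.3.1 falls back on the last available dose date. Appendix 3 (item 3) uses the data cutoff date for interim, DMC and final analyses. At database lock it uses the latest of the last visit, last dispensing, completion/discontinuation and death dates.

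Exposure is tabulated at IA 1.0 and 2.0 in both populations and also at IA 0.5 in NTDT, on "All available data up to Week 24 at the time of IA" (SAP 12.0, Tables 3 and 4). On supply, Protocol 9.3 states: "Each bottle contains 84 tablets". Bottle-level dates are already collected: SAP 13.1 cites the accountability eCRF field "Start Date of Dose From This Bottle" and a matching last-dose field.

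**The concern.** A subject who is still dosing at a data cut holds a bottle that has been dispensed but not returned. A subject who leaves and keeps the bottle is in the same position permanently. In both cases dispensed minus returned includes tablets that were not taken. The section points to a complete rule set for this situation, and that set does not contain the rule.

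The exposure summary is the dose context for the primary objective, safety and tolerability. An adherent subject could be shown at a daily dose above any the trial assigns, purely as an artefact. Total mg is most overstated, in relative terms, for subjects who took the least drug.

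**Working it through.** The documents state no exposure figure to reproduce, so this is direct arithmetic.

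**Inputs**
- 84 tablets per bottle (Protocol 9.3).
- 2 tablets a day (SAP 13.3.1).
- Dispensing interval i = 21 days in TDT (12 dispensings, Day 1 to Week 33) and 28 days in NTDT (9 dispensings, Day 1 to Week 32), from Protocol Tables 2 and 3. Need per interval is 2 × 21 = 42 and 2 × 28 = 56 tablets.
- Assumed, not stated in the documents: one bottle per dispensing visit, full adherence, visits on schedule, and no return recorded for the open bottle.

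**Formula.** Take k completed intervals and a cut d days after the latest dispensing.
- Dispensed = 84(k + 1); returned = k(84 − 2i).
- Counted as taken = 2ik + 84; actually taken = 2ik + 2d.

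**NTDT after the Week 12 dispensing (IA 0.5), k = 3**
- Dispensed 336, returned 3 × 28 = 84, counted 252.
- d = 0: 252/168 = 1.50 (+50%).
- d = 14: 252/196 = 1.286 (+28.6%).
- d = 28: 252/224 = 1.125 (+12.5%).
- At d = 0 with 150 mg tablets, average daily dose is 252 × 150/84 = 450 mg against 300. With 200 mg tablets it is 600 against 400.

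**Subjects still short of Week 24 at IA 1.0 or 2.0**
- NTDT after Week 20 (k = 5): counted 280 + 84 = 364, against 280 to 336 taken, so +30% to +8.3%.
- TDT after Week 12 (k = 4): counted 168 + 84 = 252, against 168 to 210 taken, so +50% to +20%.
- TDT after Week 21 (k = 7): counted 294 + 84 = 378, against 294 to 336 taken, so +28.6% to +12.5%.

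**Final analysis, completer with the last bottle unreturned (504 tablets taken)**
- TDT: 1008 − 11 × 42 = 546; 546/504 = 1.083 (+8.3%), or 546 × 200/252 = 433 mg/day for a nominal 400.
- NTDT: 756 − 8 × 28 = 532; 532/504 = 1.056 (+5.6%), or 532 × 200/252 = 422 mg/day.

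**Early leaver who stops on Day 14 and keeps the first bottle**
- Total: 84 counted against 28 taken, 3-fold.
- With Day 14 recorded as last dose: 84/14 = 6 tablets/day, or 900 mg/day on 150 mg tablets against 300.
- With no last-dose date, and discontinuation on about Day 51 (assumed: first call on Day 21 plus the 30 days in Protocol 8.4), the lock rule gives 84/51 = 1.65 tablets/day, or 247 mg, which is below nominal.

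**Average daily dose pulled down at an interim.** A TDT subject stops 10 days after the Week 9 dispensing, keeps the bottle and has no last-dose date; the cutoff falls at Week 24.
- Counted 3 × 42 + 84 = 210; taken 3 × 42 + 20 = 146.
- With the cutoff as last dose: 210/168 = 1.25 tablets/day, against a true 146/73 = 2.0.

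**The case against.** The strongest reply is that the plan nowhere sets a missing return to zero. SAP 10.1.1 bars imputation unless specified, and 13.3.1 leaves room for extra handling, so a programmer might well treat open bottles sensibly. This stands against saying that the plan requires every such bottle to be counted as swallowed. It does not close the gap, because the extra handling is never given.

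A reader might blame the 84-tablet bottle. Its surplus only scales the error: a bottle of exactly 42 or 56 tablets still in use at a cut would also be over-counted. With visit windows of mostly ±7 days, an NTDT interval can stretch to 42 days and use all 84 tablets.

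A reader might also extend the overstatement to the IA 1.0 and 2.0 milestone subjects, who have completed 24 weeks. The exposure rows stop at Week 24, when the bottle from Week 20 or 21 is due back. A +25% excess there (420 against 336) would require counting the bottle dispensed at Week 24 for later use, and the documents do not say that it is counted.

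Finally, the table is descriptive. The safety analyses in SAP 13.6.2 do not use tablets or mg as a denominator, and duration in weeks does not depend on the tablet count. The listings show amounts returned and per-period compliance from the CRF, so odd values could be noticed. This limits the harm; the summary figures would still be wrong.

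**Conclusion.** The concern holds in this form: a stated formula is left without the rule it needs, and applied as written it overstates total tablets and total mg whenever a bottle is open or unreturned. The effect is clearest at IA 0.5 and for subjects short of Week 24 at the later interims. It is modest for completers at the final analysis and large, in relative terms, for early leavers. The percentages depend on one bottle per dispensing visit and full adherence.

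It would be tempting to conclude that average daily dose is always inflated, and most of all in early leavers. The documents do not support that. It is inflated when the last-dose date is known, but it can fall below the true value when a cutoff or later administrative date is substituted. The direction depends on which of the two conflicting last-dose-date rules is used.

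**What to change.** In SAP 13.3.1 and Appendix 3:

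1. State that an open or unreturned bottle is not counted as fully taken. Calculate average daily dose and compliance from reconciled bottles and the days they cover. For total mg, estimate an unreconciled bottle from its start date to the last dose or cutoff date at the prescribed tablets per day, capped at the bottle content, and flag it as estimated. The adherent subjects above then show 2.00 tablets a day, and the Day 14 leaver with a recorded last dose shows 28 tablets.
2. Reconcile the last-dose-date rules in 13.3.1 and Appendix 3 item 3.
3. Report the number of subjects per arm with an unreconciled bottle.

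Simply dropping unreturned bottles is not enough: it understates total mg and gives the Day 14 leaver 0 mg.

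The same edit should correct the compliance denominator, which omits the two tablets a day. As written, full adherence gives 504/252 × 100 = 200%.

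The cost is a few sentences and a little extra programming. No new data are needed if the bottle dates are complete. The drawbacks are that the estimate assumes adherence for unreconciled bottles, and that a subject with no reconciled bottle has no average daily dose and appears only in the count under item 3.

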### **9.4. Study Drug Preparation**

### **9.5. Administration**

Subjects will be advised to take two IMR-687 or matched placebo tablets orally with food qd for 36 weeks. On days when study drug is taken in the clinic, food details will also be recorded.

## 9.6. Treatment Compliance

The investigator or designee must ensure that all subjects are adequately informed of study drug administration requirements for compliance/adherence with the study protocol.

Treatment compliance/adherence with scheduled oral administration of study drug will be assessed at the study site starting at Week 3 for TDT subjects or Week 4 for NTDT subjects; all study drug administration will be documented on the appropriate pages of the eCRF. Subjects falling below an 80% treatment compliance rate between consecutive visits will be reported as a protocol deviation.

## 9.7. Concomitant Medications

Any medication or vaccine (including over-the-counter or prescription medicines, vitamins, and/or herbal supplements) that the subject receives from the time of signing the ICF through the end of the study must be recorded along with:

- Reason for use
- Dates of administration, including start date/time and stop date/time
- Dose and frequency of administration

Subjects receiving hydroxyurea must have received it continuously for at least 6 months prior to signing the ICF, and have been on a stable dose for at least 3 months prior to signing the ICF, with no anticipated need for dose adjustments during the study including the screening period, in the opinion of the investigator.

Over-the-counter medications such as analgesics and nonsteroidal anti-inflammatory drugs that are taken on an as needed basis can be continued as long as they are not medications that interfere with metabolism, transport, or assessments (refer to [Appendix 3](#) for additional information). All concomitant medications and/or therapies must be recorded on the appropriate pages of the eCRF. Use of any prohibited medication and/or therapy must also be recorded on the eCRF and must be documented as a protocol deviation.

### 9.7.1. Non-investigational Medicinal Products

Not applicable.

### 9.7.2. Prohibited Concomitant Medications/Therapies

The investigator, in consultation with the medical monitor, will determine if any of the following concomitant medications/therapies are necessary for the well-being of the subject. The subject will be withdrawn from the study if the following are determined to be necessary:

- PDE5 inhibitors; any drugs or substances, including grapefruit juice or herbal supplements with CYP altering properties, that are known to strongly or moderately inhibit or induce CYP/CYP3A enzymes; and any drugs or substances that are substrates or significant inhibitors of P-gp or BCRP. Sensitive substrates of CYP3A4/5 are also prohibited. If there is any question as to whether a substance is permitted, please review the product labeling (if applicable), and consult the medical monitor and/or sponsor.

- Concomitant use of erythropoietin.
- Any concomitant use of sotatercept or luspatercept (Reblozyl®), or previous use within 6 months prior to randomization (Day 1).
- Any other investigational drug or device.

Because IMR-687 is a CYP3A4 substrate as well as a possible CYP3A4 inducer, caution should be employed in the co-administration of IMR-687 with other medications that are known CYP3A4 substrates. This potentially helps manage the competition for in vivo CYP3A4-mediated clearance, which could result in a DDI. This approach includes applying caution with dosing other oral medications to minimize the chance of a drug interaction at the site of absorption (e.g., the GI tract). Additional information on potential drug interactions and how to proceed can be found in Section [5.2.3](#).

Medications prohibited prior to study entry are described in the exclusion criteria in Section [8.2](#).

